1 INTRODUCTION

1.1 BACKGROUND

Pneumonia is an acute respiratory infection that affects the lungs [1]. In this disease, the alveoli (small sacs within lungs) get filled up with pus and fluid making it difficult to breathe [1]. In children under five, the most common presenting features of pneumonia are cough and /or difficult breathing/ lower chest in-drawing with or without fever [1]. Risk factors leading to pneumonia include lack of immunization, air pollution, overcrowding, parental smoking, under nutrition, non-hygienic practices, and pre-existing illnesses such as HIV and measles [2]. Early pneumonia identification and treatment saves lives as in severe cases, it can lead to death [3]. Initiating use of antibiotics upon onset of disease can hamper progression whereas absence of early intervention can have limited impacts even with intravenous antibiotics [4].

Despite the availability of standard pneumonia management guidelines and multiple global efforts, pneumonia continues to be the leading killer of children under five, accounting to around 17% of the total under five deaths globally [5-8]. It has been estimated that annually there are around 120 million episodes of pneumonia among children with around 14 million progressing to severe episodes. Out of these cases, close to 1.3 million children die with 81% of these deaths occurring in children under 2 years of age [6]. 52% of these deaths occur in the Sub-Saharan region and South Asia with main contributions from India, Nigeria, Congo, Pakistan and Afghanistan [9]. In Pakistan, pneumonia contributes to 16% of under-five mortality in the country having a well-defined yet poorly functional healthcare system [10-12].

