and KPK will have one training as their participants can be managed to be brought in one location due to close proximity. Sindh and Baluchistan participants will have two separate trainings.

3.5 Recruitment of Disguised Patients' Caregiver and Conduction of Observations:

Each data collector will be provided a pre-defined list of addresses whereby the observations will be made. He/she will go to the location and will search the nearby community for cases of pneumonia in children under five. Once the cases have been identified, their caregivers will be sought. These caregivers are the primary individuals providing direct care to the child. Usually, these are the mothers, fathers, grandmothers or guardians of the child. They will explained the purpose of the study and will be requested to participate in the study by acting as disguised caregivers to accompany the data collector to the health facilities and upon agreement will sign a consent form. This means that they will disguise as an acquaintance of the data collector who will take them to the healthcare professional to be observed. They will take the ill child along, give the history of that child to the healthcare professional and answer any relevant questions which will be asked by him/her and get the child examined and treated. In the meantime, the data collector will make the relevant observations based on the observation tool which will be filled after the visit. The data collector will not reveal that he/she is a healthcare professional. Additionally, the data collector will also take an audio recorder along to record the entire conversation which will help in filling up the observation tool later and also validate the visit. Once the visit is completed, the data collector will take the caregiver back to their premises and fill up the observation tool in tablets within one hour of the visit.

3.6 Project work-plan:

PROJECT ACTIVITIES	YEAR 1(Months)												YEAR 2
	1	2	3	4	5	6	7	8	9	10	11	12	
Ethical Clearance	X	X											
Staff Recruitment		X											
Tool Development			X										
Inception Meetings for development of implementation strategies			X										
Pretesting and Finalization of the tool				X	X								
Data Collections (Trainings, identification of study site/centers, observations)				X	X	X	X	X	X				
Data Analysis & Reporting										X	X	X	X

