4.2 INCLUSION CRITERIA

4.2.1 INCLUSION CRITERIA OF DISGUISED CAREGIVERS:

- Caregivers of children under five years of age. These are those individuals who provide direct care to the child. These could either be a mother, father, grandmother or guardian.
- The child under five under that caregiver's household must have symptoms of pneumonia/severe pneumonia as indicated in section 6.1
- Caregivers consenting to be a part of the study.

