6 STUDY ASSESSMENTS

6.1 STUDY ASSESSMENTS

The following assessments will be done while doing one time observations using the observation tool (Annex A):

1. History taking: (Did the healthcare provider inquire about the presenting complaints and the predisposing factors which might have led to the complaints)
 - ✓ Cough (presenting complaint)
 - ✓ Fast breathing (presenting complaint)
 - ✓ Laboured breathing (presenting complaint)
 - ✓ Fever (presenting complaint)
 - ✓ Immunization history (Predisposing factor)
 - ✓ Breastfeeding history (Predisposing factor)
 - ✓ Overcrowding (Predisposing factor)
 - ✓ Parental smoking (Predisposing factor)

- ✓ Air pollution (Predisposing factor)
- ✓ Nutritional history (Predisposing factor)
- ✓ Hygienic practices (Predisposing factor)
- ✓ Family history of HIV (Predisposing factor)

2. Examination:

- ✓ Temperature (For fever)
- ✓ Respiratory rate for 1 minute (For fast breathing)
- ✓ Pallor (for anemia indicating malnutrition)
- ✓ Skin rash (for measles)
- ✓ Lower chest indrawing
- ✓ Auscultation for wheeze and/or crepts

3. Diagnosis:

- ✓ Cough with no fast breathing/chest indrawing: No pneumonia
- ✓ With fast breathing and/or chest indrawing : Pneumonia
- ✓ Pneumonia with any danger signs : Severe Pneumonia

4. Management:

- ✓ No Pneumonia: Symptomatic treatment
- ✓ Pneumonia: Oral amoxicillin 40mg/kg/dose twice daily for three days
- ✓ Severe Pneumonia: For LHWs: First dose of oral antibiotic (amoxicillin) and referral to health facility and for health facilities, parenteral ampicillin 50mg/kg IV 6 hourly for five days along with gentamicin 7.5mg/kg/ IM or IV for five days.

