8.2 PROPOSED ANALYSES

Behavioural coding will be employed to prepare the data for analysis. This means that a predetermined code will be given to each variable against each category of observations (History, examination, diagnosis and treatment). Each variable will be answered as "Y" meaning yes, the task was accomplished and "N" meaning no, the task was not accomplished (section 6.1). Additionally, the responses will be labelled as correct, partially correct and incorrect for history taking and examination. If on history taking, the healthcare provider asks questions on all variables, then the responses will be labelled as correct and if any one variable is missed then the response is indicated as partially correct and in case less than 50% of the variables are asked about, then the responses will be labelled as incorrect. The same labels will be specified for the examination. In case of diagnosis and treatment, the labels will be specified as correct and incorrect only as there is no partially correct diagnosis and treatment regimens. The overall frequencies and percentages of these responses will be calculated and cross tabulated across the provinces.

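### Correct diagnosis and treatment are pooled over pneumonia and severe pneumonia, so provincial percentages can mix practice with case severity

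*Combined protocol and SAP*

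**What the plan says.** **Who is observed.** The child "must have symptoms of pneumonia/severe pneumonia as indicated in section 6.1" (section 4.2.1). The data collector "will search the nearby community for cases of pneumonia in children under five" (section 3.5). Neither section sets a quota or balance by severity.

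**How a visit is scored.** Section 6.1 and Annex C give a separate diagnosis row and management row for each class. The severe diagnosis row reads "Pneumonia with any danger signs : Severe Pneumonia", but neither place lists the danger signs. Pneumonia has one management key for every provider: "Pneumonia: Oral amoxicillin 40mg/kg/dose twice daily for three days". Severe pneumonia has a different key, which varies by provider. Section 6.1 separates LHWs from health facilities, and Annex C adds a row for BHUs.

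**How it is coded.** Items are Y or N, with N "meaning no, the task was not accomplished". There is no not-applicable code. The eCRF list in section 7.2 includes the visit checklist but no field for the child's reference class.

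**How it is analysed.** Section 8.2 says "In case of diagnosis and treatment, the labels will be specified as correct and incorrect only", and then "The overall frequencies and percentages of these responses will be calculated and cross tabulated across the provinces". No split, adjustment or separate table by severity is planned.

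**What it is for.** Section 2.1.2 makes differences between provinces the secondary objective. Section 2.2.1 lists correct diagnosis and correct treatment among the four primary endpoints.

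**The concern.** In a standardised-patient study every provider sees the same case. Here each provider sees whichever ill child was found nearby, so the case is not held constant. A pooled percentage is then a weighted average of two different tasks, and the weights are the local severity shares. Two provinces with identical practice can show different percentages, and two with different practice can show the same one.

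The pooled figure is also dominated by non-severe cases. Section 1.1 stresses that severe cases can lead to death, and section 1.2 wants the results to inform policy on mortality. The planned table would say little about how those cases are handled.

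**Working it through.** **Plan's own figure.** Section 8.1: 6 + 4 + 4 + 9 + 9 = 32 per area, and 5 × 32 = 160. Both reproduce. The sample size rests on saturation, so there is no power calculation to check.

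**Formula.** With severe share s, the pooled correct rate is (1 − s) × p_pneumonia + s × p_severe. For two provinces with identical practice, the gap is (p_pneumonia − p_severe) × (s2 − s1).

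**Size of a false gap.** The documents give neither correct rates nor local severity shares, so all of these are assumed. Shares are 5% in one province and 25% in the other.

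| Correct rate, pneumonia / severe | Pooled at 5% | Pooled at 25% | Gap |
|---|---|---|---|
| 60% / 20% | 58% | 50% | 8 points |
| 50% / 30% | 49% | 45% | 4 points |
| 70% / 10% | 67% | 55% | 12 points |
| 60% / 60% | 60% | 60% | 0 |
| 40% / 60% | 41% | 45% | −4 points |

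For example, 0.6 × 0.95 + 0.2 × 0.05 = 0.58 and 0.6 × 0.75 + 0.2 × 0.25 = 0.50.

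**Masking.** Raise both rates by 8 points in the province with 25% severe: 0.68 × 0.75 + 0.28 × 0.25 = 0.58. A province that is better in both classes then looks the same as the other.

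**Expected severe cases.** The only share in the documents is global: "annually there are around 120 million episodes of pneumonia among children with around 14 million progressing to severe episodes". That gives 14/120 = 11.7%. Applying it here is an assumption.
- All visits: 160 × 0.1167 = 18.7 (8 to 40 at shares of 5% to 25%).
- Per area: 32 × 0.1167 = 3.7 (1.6 to 8).
- By severe key in Annex C: LHW 30 × 0.1167 = 3.5; BHU 20 × 0.1167 = 2.3; all others 110 × 0.1167 = 12.8.

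At 11.7%, moving severe-case correctness from 0% to 100% shifts the pooled rate by only 11.7 points.

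**Chance differences in mix.** Take 60%/20% and s = 11.7% in both of two areas of 32.
- SD of the gap from mix alone: 0.4 × √(2 × 0.1167 × 0.8833 / 32) = 3.2 points.
- Pooled rate: 0.6 × 0.8833 + 0.2 × 0.1167 = 55.3%.
- Total sampling SE of the gap: √(2 × 0.553 × 0.447 / 32) = 12.4 points.

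The 3.2 is a component of the 12.4, not an addition to it: the binomial variance 0.247 is 0.231 within classes plus 0.016 between them. This treats visits as independent. Section 4.1 lets one caregiver serve up to three visits where cases are few, which would raise the mix component.

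**Can the class be recovered from the listed data?** If a row is marked Y, that row shows the class. If the provider is wrong, every row can be N, and nothing listed shows which row should have applied. The severe denominator is lost in exactly the visits that count as failures.

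**The case against.** The strongest reply is that the study calls itself qualitative, bases its size on saturation, and plans only frequencies and percentages, with no test or ranking of provinces. Overall guideline adherence is a legitimate descriptive quantity. That stands as a reason to keep the pooled figure as one line of the table. It does not remove the problem, because provincial difference is a stated objective and case mix distorts a descriptive percentage as it does a test.

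Several stronger readings are tempting and are not supported:

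- **A larger artefact.** Shares of 10% and 40% would give 56% v 44%, a 12-point gap at the 60%/20% rates. A 40% share in one province lies outside the 5% to 25% taken here as plausible, and nothing in the documents suggests it.
- **Bias from chance imbalance.** As shown above, this is already part of sampling error. Bias needs systematic provincial differences in severity. The documents give no figure for these, in either direction.
- **A built-in artefact between levels of care.** Section 8.2 tabulates by province only. Every area has the same planned provider mix, so the provider-specific severe key does not by itself create provincial gaps. It would matter if levels are compared under the primary objectives, where level is also tied to rural or urban setting (section 3.2).
- **Severe cases disappear.** Annex C keeps a severe row for diagnosis and for management. What is missing is a planned table and a secure denominator.

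**Conclusion.** The point holds as a conditional weakness in the analysis of two primary endpoints. Pooling lets case mix distort or hide provincial differences if the two classes are managed differently and severity differs systematically between provinces. A reasonable illustration is up to about 8 points, resting on assumed rates of 60% and 20% and assumed shares of 5% and 25%. The gap is zero with equal management and changes sign if severe cases are managed better. Independently of any bias, at a severe share near 11.7% the pooled figure is almost uninformative about severe pneumonia. A reader might infer that rewording section 8.2 is enough. It is not, because the listed fields do not record the class on which a split depends. The change should be made before data collection starts.

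**What to change.** 1. **Observation tool and eCRF.** Add one field in which the data collector records the child's reference class. Write down the definition used, since the danger signs are not listed.
2. **Scoring.** Score only the diagnosis and management row that applies, and mark the others not applicable.
3. **Section 8.2.** Tabulate endpoints 3 and 4 by class. Compare provinces within the pneumonia class, and do the same for levels and sectors if they are compared under the primary objectives. Report severe cases study-wide as counts by provider key, with an exact interval and no provincial breakdown.
4. **Reconcile the severe keys.** The BHU requirement for severe cases differs between section 6.1 and Annex C. These passages must be reconciled before any visit is scored.

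Provincial rates standardised to the study's class mix are not a workable alternative. They need a severe-case rate in every province, and an area of 32 has no severe case with probability 0.8833^32 = 2% at 11.7%, or 0.95^32 = 19% at 5%.

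**Cost.** One extra recorded item and no extra visits. Little precision is lost: about 32 × 0.8833 = 28 pneumonia visits per area remain, and at 60% correct the SE of a two-province gap is √(2 × 0.24 / 28.3) = 13.0 points, against 12.4 pooled. Small severe cells become visible. With about 19 cases and half correct, the 95% half-width is roughly 1.96 × √(0.25 / 19) = 22 points (normal approximation).

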9 OVERSIGHT ARRANGEMENTS

9.1 INSPECTION OF RECORDS

Investigators and institutions involved in the study permit trial related monitoring and audits on behalf of the sponsor, REC review, and regulatory inspection(s). In the event of audit or monitoring, the Investigator agrees to allow the representatives of the sponsor direct access to all study records and source documentation. In the event of regulatory inspection, the Investigator agrees to allow inspectors direct access to all study records and source documentation.

9.2 RISK ASSESSMENT

A study specific risk assessment will be performed by representatives of the co-sponsors, ACCORD monitors and the QA group, in accordance with ACCORD governance and sponsorship SOPs. Input will be sought from the Chief Investigator or designee. The outcomes of the risk assessment will form the basis of the monitoring plans and audit plans. The risk assessment outcomes will also indicate which risk adaptions (delete if no adaptions were possible) could be incorporated into to trial design.

9.3 STUDY MONITORING AND AUDIT

The ACCORD Sponsor Representative will assess the study to determine if an independent risk assessment is required. If required, the independent risk assessment will be carried out by the ACCORD Quality Assurance Group to determine if an audit should be performed before/during/after the study.

Risk assessment, if required, will determine if audit by the ACCORD QA group is required. Should audit be required, details will be captured in an audit plan. Audit of Investigator sites, study management activities and study collaborative units, facilities and 3rd parties may be performed.

10 GOOD CLINICAL PRACTICE

10.1 ETHICAL CONDUCT

The study will be conducted in accordance with the principles of the International Conference on Harmonisation Tripartite Guideline for Good Clinical Practice (ICH GCP).

Before the study can commence, all required approvals will be obtained and any conditions of approvals will be met.

10.2 INVESTIGATOR RESPONSIBILITIES

The Investigator is responsible for the overall conduct of the study at the site and compliance with the protocol and any protocol amendments. In accordance with the principles of ICH GCP, the following areas listed in this section are also the responsibility of the Investigator. Responsibilities may be delegated to an appropriate member of study site staff.

10.2.1 Informed Consent

The Investigator is responsible for ensuring informed consent is obtained before any protocol specific procedures are carried out.

Participant Information and Informed Consent Forms will be provided. The oral explanation to the participant will be performed by the Investigator or qualified delegated person, and will cover all the elements specified in the Participant Information Sheet and Consent Form.

The participant will be given every opportunity to clarify any points they do not understand and, if necessary, ask for more information. The participant will be given sufficient time to consider the information provided. It will be emphasized that the participant may withdraw their consent to participate at any time without loss of benefits to which they otherwise would be entitled.

The participant will be informed and agree to their records being inspected by regulatory authorities and representatives of the sponsor(s).

The Investigator or delegated member of the trial team and the participant will sign and date the Informed Consent Form(s) to confirm that consent has been obtained.

The participant will receive a copy of this document and a copy filed in the Investigator Site File (ISF).

10.2.2 Study Site Staff

The Investigator is familiar with the protocol and the study requirements. It will be the Investigator's responsibility to ensure that all staff assisting with the study is adequately informed about the protocol and their trial related duties.

10.2.3 Data Recording

The Principal Investigator is responsible for the quality of the data recorded in the CRF at each Investigator Site.

10.2.4 Investigator Documentation

The Principal Investigator will ensure that the required documentation is available in local Investigator Site files ISFs.

10.2.5 Confidentiality

All evaluation forms, reports, and other records will be identified in a manner designed to maintain participant confidentiality. All records will be kept in a secure storage area with limited access. Clinical information will not be released without the

written permission of the participant. The Investigator and study site staff involved with this study will not disclose or use for any purpose other than performance of the study, any data, record, or other unpublished, confidential information disclosed to those individuals for the purpose of the study. Prior written agreement from the sponsor or its designee must be obtained for the disclosure of any said confidential information to other parties.

10.2.6 Data Protection

All Investigators and study site staff involved with this study will comply with the requirements of the **Data Protection Act 1998** with regard to the collection, storage, processing and disclosure of personal information and will uphold the Act's core principles. Access to collated participant data will be restricted to individuals from the research team treating the participants, representatives of the sponsor(s) and representatives of regulatory authorities.

Computers used to collate the data will have limited access measures via user names and passwords.

Published results will not contain any personal data that could allow identification of individual participants.

11 STUDY CONDUCT RESPONSIBILITIES

11.1 PROTOCOL AMENDMENTS

Any changes in research activity, except those necessary to remove an apparent, immediate hazard to the participant in the case of an urgent safety measure, will be reviewed and approved by the Chief Investigator.

Amendments will be submitted to a sponsor representative for review and authorisation before being submitted in writing to the appropriate REC, and local R&D for approval prior to participants being enrolled into an amended protocol.

11.2 MANAGEMENT OF PROTOCOL NON COMPLIANCE

Prospective protocol deviations, i.e. protocol waivers, will not be approved by the sponsors and therefore will not be implemented, except where necessary to eliminate an immediate hazard to study participants. If this necessitates a subsequent protocol amendment, this should be submitted to the REC, and local R&D for review and approval if appropriate.

Protocol deviations will be recorded in a protocol deviation log and logs will be submitted to the sponsors every 3 months. Each protocol violation will be reported to the sponsor within 3 days of becoming aware of the violation. All protocol deviation logs and violation forms should be emailed to [contact]

Deviations and violations are non-compliance events discovered after the event has occurred. Deviation logs will be maintained for each site in multi-centre studies. An alternative frequency of deviation log submission to the sponsors may be agreed in writing with the sponsors.

11.3 SERIOUS BREACH REQUIREMENTS

A serious breach is a breach which is likely to effect to a significant degree:

- (a) the safety or physical or mental integrity of the participants of the trial; or
- (b) the scientific value of the trial.

If a potential serious breach is identified by the Chief investigator, Principal Investigator or delegates, the co-sponsors ([contact]) will be notified within 24 hours. It is the responsibility of the co-sponsors to assess the impact of the breach on the scientific value of the trial, to determine whether the incident constitutes a serious breach and report to research ethics committees as necessary.

